This R01 study aims to recruit 220 women across 5 sites to complete at least 176 participants. (This will accommodate a 20% screening failure and attrition rate.) Women with major depression will be recruited in the third trimester of pregnancy as verified by diagnostic measures. Subjects will be randomly assigned to UC or PIC+UC. PIC will entail that the subjects use a bright light box to expose themselves to light for 15-60 30 minutes each morning, follow an individualized sleep/wake schedule, keep a sleep/wake journal, and wear an actigraph (a wrist device resembling a wristwatch) to measure activity and light exposure throughout the day. Subjects in both groups will also have seven visits during their study enrollment, which will extend from 24-28 weeks’ gestation to eighteen weeks postpartum; At these visits, subjects will complete self-report measures and participate in mood assessments administered by a blinded clinician, their actigraph data will be downloaded and collected, and their prescribed sleep schedule will be adjusted as needed. At the beginning, middle, and end of the study, subjects will complete a sleep diary as well as provide three sets of saliva samples for evaluation of biological markers of circadian rhythm changes. The aim of this study is to assess the feasibility of integrating PIC into routine clinical care and to test whether the outcome of PIC is beneficial to both mother and infant.

Specific Aims:

Specific Aim 1: Examine the efficacy of PIC, acting through chronobiologic targets, to improve mood in women with major depression during third trimester (N=220). Hypothesis: Compared to women receiving UC for depression during pregnancy, women in the PIC+UC group will show greater improvement in dependent measures of depression (HAMD) and anxiety (HAMA) at pregnancy week 36 and postpartum week 6.

Specific Aim 2: Examine hypothesized mechanisms of change to confirm that PIC engages and alters the RDoC domains targeted by chronotherapy (specifically DLMO, Sleep Onset, Sleep Offset, Phase Angle (PA), Light Levels), and to determine whether changes in targeted domains are associated with antidepressant response. Hypothesis 2a: Compared to UC, PIC+UC patients will have earlier circadian phase and bed/wake times and shorter PA at pregnancy week 36 and postpartum week 6. Hypothesis 2b: Decrease in HAMD and HAMA scores will be mediated by changes in DLMO, sleep onset, sleep offset, phase angle, and light levels.

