Participants are randomized to usual care (UC) or personalized integrated chronotherapy (PIC)+UC. We are using urn randomization to allocate women to UC or PIC+UC while balancing for expectant mothers' parity and whether women self-identify as declining pharmacologic treatment for perinatal depression.

5) Analyses:**Specify exactly which analyses you will conduct to examine the main question/hypothesis.**

Changes in HAMD from baseline will be compared using generalized estimating equations, treating follow-up points as discrete time points, having correlated error within patient. All study time points will be in the model, but our main hypothesis will be tested as an interaction involving the baseline time point and postpartum week 6. This will be carried out within the model using orthogonal linear contrasts. Distributions for each dependent variable will be based on: a) real-world constraints, and b) model residual diagnostics. We will adjust for additional model misspecification using classical sandwich estimation.

6) Outliers and Exclusions**Describe exactly how outliers will be defined and handled, and your precise rule(s) for excluding observations.**

We will identify a data point as an outlier that should be excluded only if the value is impossible/implausible biologically or if there is corroborating evidence independent of the observation value that indicated a protocol deviation or concern related to data collection.

7) Sample Size How many observations will be collected or what will determine sample size? No need to justify decision, but be precise about exactly how the number will be determined.

We will continue enrolling through April 2024 and accept the sample size accrued at that point.

8) Other Anything else you would like to pre-register?

(e.g., secondary analyses, variables collected for exploratory purposes, unusual analyses planned?)

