The official start date of this study was 02/02/2020. Required COVID restrictions and the relocation of one of our study sites limited participant recruitment. Thus, we have changed our analytic strategy. Our original plan was to conduct an interim two-tailed analysis after 100 participants completed the study to test for early signs of confirmatory efficacy, with the plan to switch all patients to PIC+UC if the HAMD reduction between groups was significantly different at alpha=0.005 either at 36 weeks of pregnancy or 6 weeks postpartum. Absent that, we planned to use two-tailed tests of the HAMD change using an alpha of 0.02 at 36 weeks of gestation and 6 weeks postpartum. To avoid an underpowered study, we will now test a one-tailed hypothesis at 6 weeks postpartum. We are therefore registering our one-tailed hypothesis while we are still enrolling participants and collecting data to establish our new *a priori* analytic plan.

Our secondary aim is to examine putative mechanisms of change to confirm that PIC engages and alters the RDoC domains targeted by chronotherapy (specifically DLMO, Sleep Onset, Sleep Offset, Phase Angle (PA), and Light Levels) and to determine whether changes in targeted domains are associated with antidepressant response. For this aim, we hypothesize that (a) compared to UC, PIC+UC patients will have earlier circadian phase and bed/wake times and shorter PA at pregnancy week 36 and postpartum week 6; and (b) decrease in HAMD scores will be mediated by the changes in DLMO, Sleep Onset, Sleep Offset, Phase Angle, and Light Levels.

9) Name

Give a title for this AsPredicted pre-registration

Personalized Integrated Chronotherapy for Perinatal Depression NCT04364646

10) Type of study

Experiment

11) Data source

Field experiment / RCT

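### The primary GEE has no missing-data method: mood-related dropout that differs by arm could bias the week-6 contrast in either direction, slightly under most working correlations and seriously only under working independence

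*Combined protocol and SAP*

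**What the plan says.** The analysis is in the section registered with AsPredicted.org. Item 5 (Analyses) states: "Changes in HAMD from baseline will be compared using generalized estimating equations, treating follow-up points as discrete time points, having correlated error within patient". All visits enter the model, and "our main hypothesis will be tested as an interaction involving the baseline time point and postpartum week 6". The safeguard offered is: "We will adjust for additional model misspecification using classical sandwich estimation". Item 6 deals with outlying values only. No section names a working correlation, a missing-data assumption, imputation, weighting or a sensitivity analysis.

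On numbers, the Background section says: "This R01 study aims to recruit 220 women across 5 sites to complete at least 176 participants", and adds: "This will accommodate a 20% screening failure and attrition rate". Item 7 then leaves the size open: "We will continue enrolling through April 2024 and accept the sample size accrued at that point". Item 8 makes the test one-tailed: "To avoid an underpowered study, we will now test a one-tailed hypothesis at 6 weeks postpartum". No alpha is given for that test; the superseded plan used two-tailed 0.02.

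**The concern.** An unweighted GEE estimate is generally consistent when data are missing completely at random. If missingness depends on observed HAMD, the working covariance must also be close to right. The sandwich does not help here, because it corrects the standard error of an estimate that may already be shifted by who remains.

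The setting makes this worth asking. The contrast runs from V2 to V6, so a birth and four follow-up visits (V3 to V6) fall inside it. The trial is single-blind with blinded raters, and only the PIC arm has daily light and a prescribed sleep schedule. A link between mood and dropout that differs by arm is therefore plausible, although the documents do not show one.

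At stake is the single primary test. Bias towards PIC raises the false-positive rate of a one-tailed test. Bias towards UC costs power in a trial that went one-tailed because it feared having too little.

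**Working it through.** **1. The plan's own figure.** 176 / (1 - 0.20) = 220, which matches the recruitment target. The 20% covers screening failure and attrition together, so the share lost after randomisation is unknown. Power cannot be reproduced: no effect size, SD, power or one-tailed alpha is stated.

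**2. Where the bias comes from.** Take a model saturated in arm and visit, working independence, and V2 observed for everyone. The fitted value for each arm and visit is then the mean of the observed scores. For arm a, with a proportion p missing at V6, the error in that mean is

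b(a) = -p(a) x [mean of the missing - mean of the observed],

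and the bias of the contrast is b(PIC) - b(UC). Under the null, if mood drives dropout equally in both arms, the two terms cancel. If the relation differs by arm, they do not. A working correlation near the truth uses each woman's earlier scores to recover most of the loss.

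**3. Null simulation.** From the documents: visits V2 to V7, the V6-minus-V2 contrast by arm, sandwich errors, a one-sided test. Assumed: 88 per arm (176 / 2), one-sided 5%, means falling from 18 to 11, SD 4 at V2 and 6 later, and two decaying correlation patterns. Dropout is monotone and depends on the last observed HAMD, with odds multiplied by 1.65 or 2.7 per SD. It is selective on high scores in PIC, with either no selection or the opposite selection in UC. Missing at V6 is 18-24%. There were 2,000 runs per cell, so the Monte Carlo SE is about sqrt(0.05 x 0.95 / 2000) = 0.005. Negative bias favours PIC.

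| Analysis | Bias (HAMD points) | One-sided rejection |
|---|---|---|
| GEE, independence | -0.29 to -1.40 | 0.089-0.384 |
| GEE, exchangeable | -0.02 to -0.12 | 0.051-0.068 |
| GEE, AR(1) | +0.01 to -0.15 | 0.049-0.069 |
| GEE, unstructured | -0.05 to +0.03 | 0.045-0.065 |
| Likelihood repeated-measures model, unstructured | -0.04 to +0.01 | 0.044-0.066 |

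A second simulation at 88 per arm and about 20% missing gave -0.4 to -1.2 points and 12-34% under independence, and -0.02 to -0.18 points and 5-8% under exchangeable or AR(1).

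**4. What the independence figures imply.** In one cell UC dropout is unrelated to HAMD, 24% of PIC is missing and the bias is -0.74. By the formula in step 2, missing women would score 0.74 / 0.24 = 3.1 points above observed women, about half the assumed SD of 6. With the weaker slope, 0.34 / 0.19 = 1.8 points.

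**5. Variations under independence.**
- Same mood-dropout relation in both arms (500 runs per cell): bias about 0, rejection 0.042-0.058.
- Selective loss of worse-scoring women in UC instead of PIC (500 runs per cell): bias +0.55 to +0.76, rejection 0.006-0.024.
- About 10% missing in each arm, mood-related in PIC only (large-sample check): bias -0.18 to -0.39. Exchangeable gives -0.00 to -0.05.
- 50 per arm (500 runs per cell): rejection 0.100-0.302.
- About 32-39% missing (500 runs per cell): rejection 0.202-0.662.

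**The case against.** The strongest reply is that the text already describes errors as correlated within patient. The natural reading is a non-independence structure, and then the effect is slight: exchangeable and AR(1) rejection rates largely overlap those of the likelihood model. An unstructured GEE also fits the wording and does about as well. This stands, and it means the independence figures cannot be presented as what the plan will do. It does not close the point, because independence with a sandwich is a standard specification that the text does not strictly rule out.

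Second, the dropout mechanism is assumed. The discontinuations the Eligibility Criteria specify are obstetric or neonatal (fetal loss or stillbirth, birth before 36 weeks, a NICU stay over five days), and none is defined by HAMD. Visits, saliva sets and diaries fall on both arms. This also stands: the documents leave the mechanism open and do not establish it.

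Third, a reader might take the 20% as expected dropout. The Background does not support that, since it includes screening failure, and V6 is not the last visit. Likewise 176 is a target for completers, so 88 per arm is a working assumption.

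Fourth, item 5 lets the outcome distribution follow real-world constraints and residual diagnostics, which suits a bounded scale. A normal-theory mixed model is one option and need not displace the GEE. It is also biased if dropout follows unobserved mood.

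**Conclusion.** The gap is real, and its consequence is conditional. The plan relies on a sandwich that cannot correct selective dropout and leaves unnamed the choice that decides how much this matters. With about 20% missing at week 6 and arm-differential dropout on observed HAMD, the null bias is up to about 0.2 points with rejection about 5-8% under exchangeable or AR(1). Under working independence it is roughly 0.3-1.4 points, with rejection about 9-38% when it favours PIC and below 5% when it favours UC. At about 10% missing, the independence bias is about 0.2-0.4 points. All of this rests on assumed SDs, correlations, dropout slopes and a one-sided 5% level.

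A reader might infer that the primary test is invalid, or that its false-positive rate is inflated. The documents do not support that. Serious inflation needs working independence, a mood-dropout relation that differs by arm, and a direction favouring PIC, and the documents establish none of the three. Nor must dropout be unrelated to HAMD for the null contrast to be about unbiased; the same relation in both arms is enough. This is a cheap improvement, not a fatal fault.

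**What to change.** Keep the V2-to-V6 contrast and make the primary analysis valid under missing at random, using all available visits of all randomised women. Either route serves:

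- a likelihood-based repeated-measures model for HAMD at V2 to V7, arm by visit, with unstructured within-woman covariance and a stated fallback if it does not converge; or
- the GEE with a named non-independence working correlation, preferably unstructured, after arm-specific multiple imputation from earlier HAMD values, or with inverse-probability-of-dropout weights.

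State the missing-data assumption and the one-tailed alpha. Add a not-at-random sensitivity analysis, because neither route cures dropout driven by unobserved mood.

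The cost is a paragraph in the plan, no new data and a little more analysis work. The mixed model brings a normality assumption; the GEE route brings an imputation or weighting model that must itself be specified. If the primary analysis has already been run, report the addition as post hoc, with the working correlation actually used and dropout by arm and last observed HAMD.

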The 7 study center visits will include downloading of wrist monitor data, examination of sleep and activity data as measured through the actigraph versus what was reported in the sleep diary (during applicable weeks). Treatment sleep schedules will also be assigned and adjusted at study center visits. Questionnaires and blinded clinical assessments will be administered to measure mood, safety measures (e.g. suicidality and manic symptoms).

Analytic Strategy Registered with AsPredicted.org

1) Data collection:

Have any data been collected for this study already?

It's complicated. We have already collected some data but explain in Question 8 why readers may consider this a valid pre-registration nevertheless.

(Note: Choices are 'Yes, we already collected the data.', 'No, no data have been collected for this study yet.' and the answer above. Also, 'Yes' is not an accepted answer.)

2) Hypothesis:

What's the main question being asked or hypothesis being tested in this study?

The primary aim of this single-blinded RCT is to test whether adding a personalized integrated chronotherapy intervention (PIC) to usual care (UC) for perinatal depression improves mood better than UC alone in individuals who meet criteria for major depression during 3rd trimester of pregnancy. Participants are females ages 18-45 years recruited at 24-28 weeks' gestation across 5 study sites. They are enrolled between 28-30 weeks of gestation and take part in the study through postpartum week 18. After the screening and consenting visit (V1), they are randomized to UC or PIC+UC and have 6 more study visits: baseline (V2), gestational week 33 (V3), gestational week 36 (V4), postpartum week 2 (V5), postpartum week 6 (V6) and postpartum week 18 (V7). Sleep and mood are measured at Visits 2-7 and dim light melatonin onset is measured at Visits 2, 4, and 6.

Hypothesis: Compared to women receiving UC for depression during pregnancy, women in the PIC+UC group will show greater improvement in dependent measures of depression (HAMD) at postpartum week 6

3) Dependent variable:

Describe the key dependent variable(s) specifying how they will be measured.

The primary dependent variable is the score on the Hamilton Depression Rating Scale (HAMD-17) which is evaluated by blinded raters at the end of each study week. We are also measuring the Hamilton Anxiety Rating Scale (HAMA).

4) Conditions:**How many and which conditions will participants be assigned to?**

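### The primary HAMD test is an unadjusted difference in change; under stated conditions, adjusting for Visit 2 HAMD is no less precise, and over assumed correlations and SD ratios it cuts variance by about 0% to 35%

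*Combined protocol and SAP*

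**What the plan says.** Item 5 (Analyses) of the Analytic Strategy states: "Changes in HAMD from baseline will be compared using generalized estimating equations", with visits as categories and "having correlated error within patient". Every visit enters the model, and "our main hypothesis will be tested as an interaction involving the baseline time point and postpartum week 6". Standard errors come from a sandwich estimator. The distribution is open: "Distributions for each dependent variable will be based on: a) real-world constraints, and b) model residual diagnostics". No covariate and no equal-baseline constraint is named, so baseline HAMD is one level of the response. That the contrast is unadjusted is read from this silence; the plan does not use the word.

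Four other places bear on the point.
- Item 4 (Conditions): "We are using urn randomization to allocate women to UC or PIC+UC". No allocation ratio is given.
- Item 2 (Hypothesis): "After the screening and consenting visit (V1), they are randomized to UC or PIC+UC". V2, the baseline visit, comes afterwards. Study Procedures starts PIC only once V2 data collection is complete.
- Item 7 (Sample Size): "We will continue enrolling through April 2024 and accept the sample size accrued at that point".
- Item 8 (Other): "To avoid an underpowered study, we will now test a one-tailed hypothesis at 6 weeks postpartum". No alpha is stated for the new test, and no effect size, SD, correlation or power appears anywhere.

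**The concern.** A change contrast subtracts the whole baseline score, which amounts to fixing the slope of week 6 on V2 at 1. When the true slope is different, the subtraction adds noise that an estimated slope would remove. This plan moved to a one-tailed test out of concern for power and accepts whatever sample accrues, yet it makes no use of the V2 score as a covariate. Adjustment pursues the same aim without relaxing the error standard and without new data. What is at stake is precision at week 6, not validity.

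**Working it through.** **The plan's own figure.** The only sample-size arithmetic is in the Background: 176 completers with 20% loss gives 176 / 0.80 = 220. It reproduces, but it says nothing about the precision of this contrast.

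**Inputs.** From the documents: the form of the contrast, the one-tailed test, the entry cut of HAMD-17 ≥ 14, and V2 after randomization but before PIC. Assumed: r (correlation of V2 with week 6 HAMD) from 0.3 to 0.7; k (SD at V2 / SD at week 6) from 0.6 to 1.0; one-sided alpha 0.05 for the power illustration.

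**Step 1. What the contrast is.** In a simulated complete data set (176 women, six visits, identity link), the GEE group-by-visit interaction was −0.5645 with robust SE 0.9304, under both independence and exchangeable working correlation. The plain difference in mean change gave the same two figures.

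**Step 2. Variances.** Set the week 6 SD to 1. Large-sample variance is then proportional to
- change contrast: 1 + k² − 2rk
- adjusted for V2: 1 − r²

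The gap is (k − r)², which is never negative. The proportional reduction in variance is (k − r)² / (1 + k² − 2rk). At r = 0.3, k = 1 it is 0.49 / 1.40 = 35%, or 1 − √0.65 = 19% in standard error. At r = 0.5, k = 0.6 it is 0.01 / 0.76 = 1.3%. It is zero when k = r.

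| Variance reduction | r = 0.3 | r = 0.5 | r = 0.7 |
|---|---|---|---|
| k = 1 | 35.0% | 25.0% | 15.0% |
| k = 0.75 | 18.2% | 7.7% | 0.5% |
| k = 0.6 | 9.0% | 1.3% | 1.9% |

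**Step 3. Missing week 6 scores.** Let a fraction d be missing and give the plan its most favourable working covariance. The reduction becomes (k − r)² / [(1 − r²)/(1 − d) + (k − r)²]. With d = 0.2 assumed, it is 30/21/12% at k = 1, 15/6/0.4% at k = 0.75 and 7/1/1.5% at k = 0.6.

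**Step 4. Power.** If the adjusted test has 80% power, the change contrast has Φ[(1.645 + 0.842) × √(1 − reduction) − 1.645]. This gives 64/69/74% at k = 1, 73/77/80% at k = 0.75 and 77/80/79% at k = 0.6.

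**Step 5. The entry cut.** For a normal score cut at its mean, or 1 SD below it, the remaining SD is 0.603 or 0.794 of the uncut SD. If the week 6 SD equals the uncut SD, k is about 0.60 to 0.79. At k = 0.794 the reduction is 21.1/10.3/1.7% for r = 0.3/0.5/0.7. The cut also lowers r, and at r = 0.2 the reduction is 27%. If the cut was applied at V1, V2 is restricted only indirectly and k is nearer 1.

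**Step 6. Missing V2.** Take a fraction m = 10% missing at random, k = 0.6, r = 0.5, and the planned GEE under independence.
- Change contrast: 0.36/0.9 + 1 − 0.6 = 0.800.
- Adjusted, dropping women without V2: 0.75/0.9 = 0.833 (ratio 1.04).
- Adjusted, missing V2 set to the mean of all observed V2 scores: 1 − 0.25 × 0.9 = 0.775 (ratio 0.97).

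The least favourable case found is r = 0.7 against a fully efficient planned covariance: 0.559 / 0.540 = 1.03.

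**Step 7. Small samples and unequal allocation.** Estimating the slope costs about 1/(N − 4): 1.0% at N = 100 and 0.6% at N = 176. With 2:1 allocation, slopes of 1.5 and 0.5, and V2 and residual variances of 1, the variances are 5.63 for change, 6.00 with a common slope and 5.50 with arm-specific slopes.

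**The case against.** The strongest objection concerns V2 itself. It follows randomization, possibly by several weeks, in a single-blind trial, so women may know their arm when V2 HAMD is rated. Suppose assignment shifts V2 by t2 and week 6 by t6. The planned contrast then targets t6 − t2 and the adjusted one targets t6 − (r/k)t2. At r = 0.5, k = 1 these differ by half a point for each point of t2, and a comparison of precision is no longer like for like. This stands as a condition on the claim. It does not favour the plan, because neither analysis recovers t6 in that case.

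It can also be said that change and covariance adjustment are both accepted analyses, and that the registered contrast matches the hypothesis of greater improvement. That is right, and it is why no error is alleged. With an identity link, and V2 unaffected by assignment, the adjusted difference estimates the same effect in HAMD points.

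Timing is a fair challenge. With enrolment through April 2024, V1 at 24 weeks or later and delivery at 40 weeks assumed, the last week 6 visit fell 16 + 6 = 22 weeks later, about October 2024. The cover page shows an upload in October 2025. The documents do not say whether outcomes have been analysed by arm, so the window may have closed, but this is not established.

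A reader might infer that the planned test is biased, or that the trial forgoes 35% of its information. The documents support neither. The contrast is unbiased under randomization, and 35% is one corner of an assumed grid. Nor is 35% a ceiling: r = 0.3 with k = 1.2 gives 47%.

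**Conclusion.** The point holds as a conditional statement about efficiency. With an identity link, near-complete V2 data, 1:1 allocation or equal baseline slopes, and V2 HAMD unaffected by assignment, adjustment is no less precise in large samples. The documents establish none of the four: the distribution is left open, the allocation ratio is not given, and V2 comes after randomization. The last condition is plausible because PIC has not begun at V2, but it remains an assumption.

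For r of 0.3 to 0.7 and k of 0.6 to 1.0, variance falls by about 0% to 35%. The lower part is more likely if the entry cut compresses V2; a correlation below 0.3 would raise the gain. A reader might also infer that adjustment would have made the one-tailed test unnecessary. Without r, k, alpha, an effect size or the final N, that cannot be judged. The point is worth considering, with medium confidence.

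**What to change.** State that the primary treatment difference at postpartum week 6, in HAMD points, comes from a GEE on V3 to V7 with treatment × visit and centred V2 HAMD × visit, identity link and robust standard errors. Then specify the following.
- Use a small-sample correction such as Mancl-DeRouen if N is near 100.
- Replace a missing V2 score by the mean of all observed V2 scores, ignoring arm and outcome, so that no woman is dropped.
- Use arm-specific centred slopes if allocation is not 1:1.
- Report the registered change contrast as a sensitivity analysis.
- Compare V2 HAMD between arms as a check on the assignment condition.

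Record the change before any outcome is analysed by arm. If that has already happened, keep the registered contrast as primary and report the adjusted estimate beside it, labelled post hoc.

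The cost is a second change to the primary analysis, five baseline-by-visit slopes (ten if arm-specific), and a variance increase of about 1% to 3% in the least favourable cases. No new data are needed.

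### The primary GEE contrast relies on an uncorrected sandwich variance with no guaranteed sample size: a small anti-conservative bias that a one-phrase change removes

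*Combined protocol and SAP*

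**What the plan says.** The primary analysis is in the Analytic Strategy, item 5: "Changes in HAMD from baseline will be compared using generalized estimating equations, treating follow-up points as discrete time points". All visits enter the model, and "our main hypothesis will be tested as an interaction involving the baseline time point and postpartum week 6". On the variance it says: "We will adjust for additional model misspecification using classical sandwich estimation". It names no finite-sample correction, no normal or t reference and no working correlation. It leaves the outcome distribution to real-world constraints and residual diagnostics.

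Item 7 sets the sample size by date: "We will continue enrolling through April 2024 and accept the sample size accrued at that point". It gives no target and no minimum. The Background section still carries the planning figure: "This R01 study aims to recruit 220 women across 5 sites to complete at least 176 participants".

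Item 8 reports that recruitment was limited and gives the consequence: "To avoid an underpowered study, we will now test a one-tailed hypothesis at 6 weeks postpartum". It states no alpha for that test. The levels it mentions belong to the superseded plan, for example "Absent that, we planned to use two-tailed tests of the HAMD change using an alpha of 0.02".

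**The concern.** The sandwich variance is justified as the number of independent clusters becomes large. Here each woman is a cluster. In a finite sample her residual is pulled towards zero because she helped to fit her own arm's mean, so the classical estimator is too small on average. A normal cut-off adds to this by treating the estimated variance as known.

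Both effects act in the same direction: the interval for the HAMD contrast is slightly too narrow, and the test rejects slightly too often under the null. The plan chooses a large-sample estimator in the same document that gives up a fixed sample size. It should therefore either guarantee enough women for the bias to be negligible or remove the bias.

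**Working it through.** **Inputs from the documents.** Two arms; six mood assessments (Visits 2 to 7); arm-by-time contrast of baseline against postpartum week 6; classical sandwich; one-tailed test; planning target of 220 recruited and 176 completers.

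**Planning figure.** 176 / (1 - 0.20) = 220, which agrees with the stated target and its 20% allowance. The plan gives no power, effect size, SD or alpha for the revised test, so there is nothing further to reproduce.

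**Assumptions.** Equal arms of n = N/2; Gaussian outcome with identity link; N from 40 to 176; one-sided alpha of 5%, with 2.5% and 2% as alternatives.

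**Step 1: bias of the standard error.** With complete data in a saturated arm-by-visit model, the contrast is the difference between arms in mean change. The classical sandwich divides each arm's sum of squares by n where the unbiased estimator divides by n-1. The standard error is therefore multiplied by r = sqrt((n-1)/n):
- N=40: sqrt(19/20) = 0.9747, 2.5% low
- N=60: sqrt(29/30) = 0.9832, 1.7% low
- N=100: sqrt(49/50) = 0.9899, 1.0% low
- N=176: sqrt(87/88) = 0.9943, 0.6% low

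**Step 2: actual one-sided error.** With a normal cut-off it is P(T > z·r), where T has a t distribution on N-2 degrees of freedom. With a t cut-off and no correction, the t quantile replaces z. At N=40 and nominal 5%, z·r = 1.645 × 0.9747 = 1.603, and the upper tail of t on 38 df beyond that point is 0.0586.

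| N | z, 5% | z, 2.5% | z, 2% | t, uncorrected, 5% |
|---|---|---|---|---|
| 40 | 5.86% | 3.18% | 2.62% | 5.43% |
| 60 | 5.56% | 2.94% | 2.40% | 5.28% |
| 80 | 5.42% | 2.83% | 2.30% | 5.21% |
| 100 | 5.33% | 2.76% | 2.24% | 5.17% |
| 176 | 5.19% | 2.65% | 2.13% | 5.10% |

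**Step 3: incomplete data.** The closed form assumes complete data, so it was checked by simulating the GEE. The settings were six visits, exchangeable working correlation, a different true (autoregressive) correlation, two baseline covariates and 20% monotone dropout, with 6,000 runs per setting and a Monte Carlo error of about 0.2 points. With z at nominal 5%, the error was 5.8% (N=40), 5.8% (60), 5.6% (80), 5.4% (100) and 5.5% (176). Skewed errors with 30% dropout gave 5.9%, 5.9% and 5.3% at N=40, 60 and 100. The direction is the same throughout and the size is similar. Differences between neighbouring sizes are within or close to simulation noise.

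**Step 4: effect of a correction.** In the balanced complete-data case, Kauermann-Carroll multiplies the classical standard error by 1/r, which restores the unbiased value. With t on N-2 df the error is then exactly 5%. Mancl-DeRouen multiplies it by 1/r², which overshoots: with t the error is 4.6% at N=40 and 4.8% at N=100. In the simulations with normal errors and 20% dropout, Mancl-DeRouen with t gave 4.4% at N=40 and 4.8% to 5.2% at the larger sizes.

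**The case against.** The strongest reply is that the effect is too small to matter. At nominal 5% the excess is below one percentage point at every size examined, and about 0.2 points by closed form at the planned 176 completers. That stands, and it sets the severity.

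Three further replies also stand:
- **No reference distribution is given.** The normal cut-off is an assumption. A t reference alone removes roughly half of the excess.
- **No alpha is given.** Any nominal level for the revised test is the reader's assumption. This is a larger gap than the variance bias.
- **No accrued number is given.** A reader might infer from the limited recruitment that the trial will end with only a few dozen women. Item 8 does not say how far recruitment fell short, so the smaller sizes above are illustrations and not a forecast.

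The objection does not remove the point itself. The bias always favours rejection, and a t reference without a corrected variance still leaves some excess. Item 5 is also the place for specifying the analysis exactly. Leaving the variance correction and the reference distribution open leaves a choice to the analyst, in a plan revised after data collection began.

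**Conclusion.** This is a minor but real weakness. As written, the primary standard error is low by about 0.6% to 2.5% for N from 176 down to 40. The actual one-sided error at an assumed 5% is about 5.2% to 5.9% with a normal reference, or 5.1% to 5.4% with t. These figures assume equal arms, complete data and a Gaussian identity-link model. Simulation with dropout and covariates gave similar values.

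Several stronger readings are tempting but unsupported:
- **That the primary test is invalid or seriously inflated.** The figures above do not show this.
- **That there are only five clusters because there are five sites.** Item 5 places the correlation within patient, so the number of clusters is the number of women.
- **That the move to a one-tailed test causes the problem.** The bias is in the variance estimator and is present whichever tail is tested.
- **That the secondary analyses share the fault.** Item 8 names no model for the secondary aim, so this cannot be said from the documents.

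**What to change.** In item 5, replace the classical sandwich with a bias-corrected one, and name it. Kauermann-Carroll is preferable because it is exact with t in the balanced complete-data case. Mancl-DeRouen is acceptable but mildly conservative. State that the week-6 contrast is tested against a t distribution on about N-2 degrees of freedom, and give the one-sided alpha in the same edit.

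The cost is a short change of wording and a software option. Relative to the classical estimate with complete data, the standard error rises by 1.0% (N=100) to 2.6% (N=40) with Kauermann-Carroll, since 1/r = 1.010 and 1.026. With Mancl-DeRouen it rises by 2.0% to 5.3%, since 1/r² = 50/49 and 20/19. The t cut-off is also slightly larger than the normal one. Together these give up a little power, which deserves acknowledgement in a trial that changed its plan to avoid being underpowered.
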